#### 12.5 Methods

**12.5.1 Samples** 

12.5.1.1 Obtaining, labelling, storing

Following informed consent, blood samples will be collected into vacutainer systems or similar tubes (usually 2 x 10 ml EDTA vacutainers) on D1 and D14/D15 of the study. The collected blood should be centrifuged, processed and stored at -80 $^{\circ}$ C according to the NeoART- trial: Blood sample collection, processing and storage SOP . NB. The Sponsor representative should be notified in instances where the storage freezer temperature deviation from -80 $^{\circ}$ C by more than +/-10 $^{\circ}$ C

These samples will be used for genomic and proteomic analysis. Blood samples will be suitably stored in the pathology department of each site till required for batch analysis. When requested for batch analysis at various recruitment time points throughout the study, blood samples will be transferred for centralised study sample storage under the Human Tissue Authority License/ Permit to Import or Export of Human Tissues or Part Thereof Health Office/District Health Office (BLESS)

The Sponsor 'Record of retained body fluids log' will be maintained throughout the study at each site to track all participant blood and Tumour samples accountability and location. These completed logs should be made available upon request at study monitoring visits.

Tumour samples will be derived from tumour biopsies performed during colonoscopy and surgical samples following surgery. Any excess tumour tisue left over after the tissue sample has been processed for routine diagnostic purposes will be utilised. Formalin fixed, paraffin embedded blocks will be prepared and stored in the pathology department of each site till requested for batch analysis. All tissue samples will be transferred for centralised study sample storage under the Human Tissue Authority License/ Permit to Import or Export of Human Tissues or Part There of Health Office/District Health Office (BLESS).

Each sample will be coded with the unique participant study ID to maintain confidentiality. The date of collection will also be recorded on study sample log and the relevant CRF completed. The samples will be stored indefinitely, with patient consent. However patients have the right to have the samples destroyed by contacting the Chief Investigator who will then arrange for the samples to be confidentially destroyed. Tumour samples will be analysed to identify tumour markers predictive of response to artesunate and elucidate potential mechanisms of action. Samples will be sent for further molecular analyses to the labs of other collaborators involved in the NeoART project collaboration in accordance with the NeoART-M Material Transfer Agreement (MTA).

Patient treatment allocation blinding will be maintained throughout the trial including during the substudy biomarker/mechanism of action analysis. An independent lab researcher will de-link the patient sample from the trial patient ID and allocate the sample a separate random study sample lab number. Once the serum and tissue samples have been processed, the exploratory molecular endpoint results

will be entered into a lab results excel spreadsheet. The sponsor will then be provided with the delinked study sample lab number and they will notify the independent lab researcher of the study arm allocation for each de-linked study sample.

#### 12.5.1.2 Transporting samples

An approved specialised courier will transfer the samples at the appropriate temperature (e.g. -80°C for specimens stored at -80 °C) with in-transit monitoring and transport labelling of specimens. Arrangements for confirmation of receipt will be clearly outlined and logged on. A copy of this will be kept within the Trial Master File.

#### 12.5.1.3 Laboratory procedures

The CI or the CI delegate will ensure that any laboratory that is used for the trial is adequate for "the foreseen duration of the trial to conduct the trial properly and safely" (ICH GCP 4.2.3 and ICH GCP 5.184b). The CI or the CI delegate will ensure that the laboratory the study will use has been verified and is compliant with accreditation standards and that all necessary contracts for the contracted activities have been finalised. The CI or the CI delegate will ensure that any laboratory used for research purposes sets up and maintains a study specific Laboratory Site File that contains a current approved version of the protocol. Access to the laboratory files will be provided to the Sponsor trial monitor. ct s

Samples will be stored and shipped to any external labs involved in the NeoART project collaboration according to the agreed NeoART Material Transfer Agreement (MTA). Each sample will be coded with the participants Trial ID to maintain confidentiality. The date of shipping of the samples will be recorded on the Sample Collection Log.

#### 12.6 Radiology or any other procedure(s)

Patients will have a routine baseline CT Chest/Abdomen/Pelvis as part of their staging investigations prior to entering the study. Following surgery they will have a routine restaging CT Chest/Abdo/Pelvis at 1 year, 2 year and 5 year follow up visits to exclude disease recurrence as per routine clinical follow up.

# 13. Translational research / Pharmacodynamic Studies

For instructions on processing and storage of study bloods, tissue samples please refer to the study lab manual.

# 14. Pharmacovigilance

#### 14.1 Definitions

**Adverse Event (AE)** — Any untoward medical occurrence in a patient or clinical investigation subject administered a pharmaceutical product and which does not necessarily have to have a causal relationship with this treatment.

An adverse event (AE) can therefore be any unfavourable and unintended sign (e.g. an abnormal laboratory finding), symptom or disease temporally associated with the use of a medicinal product, whether or not considered related to the medicinal product. Pre-existing conditions should only be reported as an adverse event if the condition worsens by at least 1 CTCAE grade. As the IMP has a short half-life, we would expect drug clearance within 24 hours of stopping the IMP.

As part of pharmacovigilance, adverse event data will be collected from the day 1 of IMP dose until 4 weeks following the end of the IMP 14 day treatment schedule. This coincides with the D42 post surgical review.

**Adverse Reaction (AR)** — All noxious and unintended responses to a medicinal product related to any dose should be considered adverse drug reactions.

**Serious Adverse Event (SAE)** or Serious Adverse Reaction (SAR) — any untoward medical occurrence that at any dose:

- Results in death,
- Is life-threatening,
- Requires inpatient hospitalisation or prolongation of existing hospitalisation,
- Results in persistent or significant disability/incapacity or
- Is a congenital anomaly/birth defect.

Medical and scientific judgement should be exercised in deciding whether expedited reporting is appropriate in other situations, such as important medical events that may not be immediately lifethreatening or result in death or hospitalisation but may jeopardise the patient or may require intervention to prevent one of the other outcomes listed in the definition above. These should also usually be considered "serious".

Suspected Unexpected Serious Adverse Reaction (SUSAR) — an Adverse Reaction which is classed in nature as both serious and unexpected

An 'Unexpected Adverse Reaction' is when both the nature and severity of the event is not consistent with the reference safety information available for the IMP in question.

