**Medical History** 

Concomitant medication and patient self reported adverse events

QOL –questionnaires – EuroQol EQ-5D, EORTC QLQ C-30, QLQ-CR29

Day 14 of study medication/Pre-operative admission assessment

Medical history

Concomitant medication and patient self reported adverse events

QOL –questionnaires – EuroQol EQ-5D, EORTC QLQ C-30, QLQ-CR29

Day 15 Surgery

Blood tests – FBC, Kidney and liver function tests, CEA tumour marker

Post treatment serum sample for study molecular analyses, these blood tests will be done on either day 14 or 15.

Safety blood tests (FBC, U&E, LFT) must be available prior to patients having surgery to exclude risk of neutropenia and deranged biochemistry.

Post surgery/in-patient stay/or at a relevant time point in the case of cancellation of surgery Patient self-reported adverse events.

Day 28

Blood test - FBC

Day 42 (Routine follow up 4 weeks post surgery)

Medical history

Blood tests – FBC, Kidney and liver function tests, CEA tumour marker

6 month follow up visit post surgery Medical history Blood tests – CEA tumour marker 12 month follow up visit post surgery Medical history Blood tests – CEA tumour marker Colonoscopy CT scan chest, abdomen and pelvis

18 month follow up visit post surgery Medical history Blood tests – CEA tumour marker

24 month follow up visit post surgery Medical history Blood tests – CEA tumour marker CT scan chest, abdomen and pelvis

30 month follow up visit post surgery Medical history Blood tests – CEA tumour marker

36 month follow up visit post surgery Medical history Blood tests – CEA tumour marker

42 month follow up visit post surgery Medical history Blood tests – CEA tumour marker

48 month follow up visit post surgery Medical history Blood tests – CEA tumour marker

54 month follow up visit post surgery Medical history Blood tests – CEA tumour marker

60 month follow up visit post surgery Medical history Blood tests – CEA tumour marker CT scan chest, abdomen and pelvis

At the end of 5 years follow up patients with no evidence of disease recurrence will be discharged back to the care of their GP. All patients with disease recurrence will have their management discussed at the Colorectal Multidisciplinary meeting (if available).

For pragmatic trial management, the following visit windows are permitted:

Day 1 and Day 7 -/+3 days of the study review date. Any baseline blood tests within 1 week of starting the study treatment are acceptable.

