#### 14.2 Investigator responsibilities relating to safety reporting

All Adverse Events whether serious or not will be recorded in the hospital notes in the first instance. A record will also be kept in the participant's CRF and the Sponsor's AE Log. In the event of a mildly deranged blood test or clinical observation of no clinical significance to the patient (for example a mildly elevated liver function test or a mildly elevated blood pressure reading in a participant with known hypertension taking prescribed antihypertensive medication), the local PI will be informed and will sign and date the participants CRF. However it will not be necessary to complete an AE CRF or the Sponsor's AE Log for these minor events.

SAEs and SARs must be notified to the sponsor as soon as the investigator becomes aware of the event (within 24 hours). Refer to sponsor's SOP and ensure the completed SAE report form is sent to the sponsor via E-mail.

The sponsor will inform the National Pharmaceutical Regulatory Agency (NPRA) and relevant ethics committee of SAE and SUSARs as soon as possible, but no later than 7 calendar days after first knowledge by the sponsor that a case qualifies. Any additional information will be reported within 8 additional calendar days. This report must include an assessment of the importance and implication of the findings, including relevant previous experience with the same or similar medicinal products. Follow-up information should be actively sought and follow-up reports should be submitted to the NPRA when it becomes available.

Causality Assessment — All cases judged by either the reporting health care professional or the sponsor as having a reasonable suspected causal relationship to the medicinal product qualify as ARs.

**Definitely** — there is clear evidence to suggest a causal relationship, and other possible contributing factors can be ruled out.

**Probably** — there is evidence to suggest a causal relationship and the influence of other factors is unlikely.

**Possibly** — there is some evidence to suggest a causal relationship (e.g. the event occurred within a reasonable time after administration of the trial medication). However, the influence of other factors may have contributed to the event (i.e. the patient's clinical condition, other concomitant events).

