#### 15.2 Data collection tool

Case Report Forms will be designed by the CI and the CI delegate and the final version will be approved by the Sponsor.

It is the Investigator's responsibility to ensure the accuracy of all data entered and recorded in the CRFs. The Staff Delegation of Responsibilities Log will identify all trial personnel responsible for data collection, entry, handling and managing the database. Basic demographic and clinical information will be gathered at the time of the initial interview and by review of the medical notes if needed. The following information will be recorded for all subjects in the CRF:

- Demographic details: Date of enrolment, age, gender, ethnicity
- Clinical data: symptomatology, risk factors for development of CRC, weight, height, vital signs
- Findings at endoscopy
- Imaging: findings of ultrasound, CT and/or MRI (performed as clinically indicated)
- Disease staging: TNM staging prior to surgery and definitive histological staging (TNM, Duke's stage)
- Histology: routine histological grading, apoptosis count and specialist assays (see below)
- Concomitant medication: a full record of all non-study drugs taken will be kept
- Study-drug treatment: compliance with study medication, all adverse events, serious or otherwise
- Validated Quality of Life Tool (EORTC QLQ C-30, EuroQol EQ-5D, QLQ-CR29)

The following blood sample analysis will be performed:

- Baseline FBC, urea and electrolytes, LFTs, CEA, pre-treatment serum sample for study molecular analyses
- Day 14/15 of treatment FBC, urea and electrolytes, LFTs, CEA, post-treatment serum sample for study molecular analyses
- Day 28 FBC
- Day 42 (4 weeks post-surgery) FBC, urea and electrolytes, LFT, CEA
- 6 monthly visits for 5 years following surgery CEA
- Serum plasma samples will be taken at baseline (Day 1) and end of treatment (Day 14), processed and stored at -80°C (+/- 10°C) for future analyses
- Any other blood or clinical sample at any time if deemed necessary by the investigators in case of a suspected adverse event

All laboratory analysis should be reviewed by the PI and where results reported are not within the normal range the PI must clearly annotate 'Not clinically Significant' or 'Clinically Significant' and sign and date the results. The relevant results should be carefully transcribed to the Case Report Forms.

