#### Toxicity assessments

The proportion of patients experiencing grade 3 or 4 toxicity will be compared between the two treatment arms using the chi-squared test. When cell frequencies are less than 5, Fisher's exact test will be used. The chi-squared test for trend will also be used to compare all toxicity scores.

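### Adverse-event collection runs to Day 42, but no enquiry is listed after the in-patient stay, and mild laboratory changes may stay off the log that an all-grade comparison could use

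*Protocol*

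**What the plan says.** Section 14.1 sets the safety window: "adverse event data will be collected from the day 1 of IMP dose until 4 weeks following the end of the IMP". The course lasts 14 days. The section then names the visit that closes the window: "This coincides with the D42 post surgical review".

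Section 12.3 lists patient-reported adverse events at Day 7, at Day 14 and after surgery during the in-patient stay. The Day 28 entry is a full blood count (FBC) only. The entry headed "Day 42 (Routine follow up 4 weeks post surgery" contains a medical history, FBC, kidney and liver tests and CEA, with no adverse-event item. The Appendix 2 chart has no adverse-event row at any visit.

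Section 14.2 first sends every adverse event, serious or not, to the hospital notes, the CRF and the AE log. It then makes an exception. "In the event of a mildly deranged blood test or clinical observation of no clinical significance to the patient", the local investigator is told and signs the CRF, but "it will not be necessary to complete an AE CRF" or the log. Section 15.2 lists all adverse events among the CRF data and says of laboratory reports: "The relevant results should be carefully transcribed to the Case Report Forms".

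The toxicity paragraph of 17.3.3.3 compares grade 3 or 4 events by a chi-squared test and adds: "The chi-squared test for trend will also be used to compare all toxicity scores". It does not name the data source for those scores.

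**The concern.** Toxicity, adverse events and surgical morbidity are all secondary endpoints (5.1, 17.2.2). What the visit list asks for stops short of the window in 14.1. After discharge, a symptom or a complication managed without readmission reaches the CRF only if the patient volunteers it or the site asks unprompted. The interim reviews are triggered by completed Day 28 assessments (17.3.3.1) or Day 42 assessments (17.5, feasibility and tolerability), and neither visit carries an adverse-event item.

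The second strand is the exemption. Section 14.1 counts an abnormal laboratory finding as a possible adverse event, and 14.2 and 15.2 ask for all of them. The exemption then removes mild ones by local judgement, with no CTCAE threshold for what counts as mild. A trend test over all grades needs the low grades recorded alike at every site. If sites differ, or if low grades are thinned in both arms, a true difference between artesunate and placebo becomes harder to see.

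**Working it through.** **1. The window.** Last dose on Day 14, plus 4 weeks: 14 + 28 = Day 42. This reproduces the end point stated in 14.1. The Day 42 visit may be held within 2 weeks either way (12.3), so from 42 − 14 = Day 28 to 42 + 14 = Day 56. An early visit would come before the window closes.

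**2. Window against schedule.**

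| Contact | Section 12.3 | Appendix 2 |
|---|---|---|
| Day 7 | Medical history and, separately, adverse events | No adverse-event row |
| Day 14 | Medical history and, separately, adverse events | No adverse-event row |
| After surgery, in-patient | Adverse events | No adverse-event row |
| Day 28 | FBC only | Combined FBC/renal/liver row marked |
| Day 42 | Medical history and bloods | Medical history and bloods marked |

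At Day 7 and Day 14 history and adverse events are separate items. A history alone at Day 42 is therefore not clearly the adverse-event enquiry. The 6- to 60-month visits also list a history, after adverse-event collection has ended.

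**3. Length of the stretch without a listed enquiry.** Surgery is on Day 15, so 42 − 15 = 27 days remain to Day 42. The protocol gives no length of stay. With an assumed stay of L days, the share of those days after discharge is (27 − L)/27:

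- L = 3: 24/27 = 89%
- L = 7: 20/27 = 74%
- L = 14: 13/27 = 48%

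This describes the schedule. It is not an estimate of events lost, because a question at Day 42 would look back over the whole stretch.

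**4. What equal under-recording would do.** The protocol gives no toxicity rates, so the following is illustration only. Assume 100 patients per arm, a two-sided 5% test of two proportions, and the same fraction s of events recorded in both arms. With p1 = s × placebo rate, p2 = s × artesunate rate, m = (p1 + p2)/2 and n = 100:

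power = Φ( [ |p2 − p1| − 1.96 √(2m(1 − m)/n) ] / √( [p1(1 − p1) + p2(1 − p2)]/n ) )

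| Assumed true rates | s = 1 | s = 0.8 | s = 0.6 | s = 0.5 |
|---|---|---|---|---|
| 10% v 25% | 0.80 | 0.69 | 0.55 | 0.47 |
| 15% v 30% | 0.72 | 0.60 | 0.46 | 0.39 |
| 20% v 40% | 0.88 | 0.76 | 0.60 | 0.51 |

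For 10% v 25% at s = 0.6, the recorded rates are 6% and 15%, and the recorded difference shrinks from 15 to 9 percentage points. The table shows the direction and the sensitivity. Nothing in the protocol says what s would be.

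**The case against.** The strongest reply is that Day 42 is a collection point by the protocol's own words. Section 14.1 ties the end of collection to that review, the visit includes a history, and 14.2 and 15.2 require all adverse events on the CRF. On this view 12.3 merely lacks a label. Many sites would probably ask anyway, so the argument stands against any claim that events will be lost. It does not remove the mismatch, because 12.3 names adverse events separately wherever it wants them asked.

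The chart is also weak evidence by itself. It has no adverse-event row even for Day 7 and Day 14, where 12.3 does list the enquiry. It carries no 12-month CT mark although 12.3 and 12.6 schedule that scan, and its pregnancy-test row is empty. The chart is incomplete generally, so the finding rests mainly on 12.3.

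A reader might infer that delayed blood toxicity goes unseen. The documents do not support that. An FBC is scheduled at Day 28 and Day 42, with renal and liver tests at Day 42, and the investigator must mark each out-of-range result as clinically significant or not and sign it (15.2). Neutropenia and haemolytic anaemia, the main risks named in 6.12, are what the counts target. Events needing admission are serious and reportable within 24 hours, and all deaths are reported.

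A reader might also infer that low-grade toxicity is under-counted as a matter of fact and that tolerability will look better than it is. That goes too far. The exemption is limited to mild changes of no clinical significance, and relevant results still reach the CRF. The toxicity paragraph names no data source, and a statistical analysis plan could choose the CRF values. The laboratory strand is therefore conditional on the AE log being used. An analysis plan cannot, however, recover symptoms that nobody asked about, or values never entered on the CRF.

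**Conclusion.** The point holds as a risk created by an inconsistency between sections. The visit list in 12.3 does not carry out the window in 14.1, and the exemption in 14.2 sits uneasily with the requirement in 14.2 and 15.2 to record all adverse events. The data exposed are non-serious, non-laboratory events between discharge and Day 42 and, only if the trend test uses the AE log, low-grade laboratory toxicity. Late haematological effects are largely covered.

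The size of any under-count cannot be computed from the protocol. The 48% to 89% range depends on an assumed stay of 14 down to 3 days, and the power table depends on assumed rates and equal under-recording in both arms. The primary endpoint is not affected. It should be corrected, because the safety comparisons and the tolerability reviews rely on these visits and the remedy is cheap.

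**What to change.** - **Section 12.3 and Appendix 2:** add an adverse-event enquiry at Day 42 and at the Day 28 contact, and add an adverse-event row to the chart covering Day 7, Day 14/15, the in-patient stay, Day 28 and Day 42.
- **Section 17.3.3.3:** state that laboratory toxicity is graded for every patient from the scheduled values: FBC, renal and liver tests at baseline, Day 14/15 and Day 42, and FBC at Day 28. Sections 12.3 and 15.2 give FBC only at Day 28 while Appendix 2 marks the combined blood row, so these must first be reconciled. With grades taken from values, the exemption in 14.2 can remain for the log.
- **Section 15.2:** require all these scheduled values on the CRF. Transcribing only relevant results does not assure a grade for every patient.
- **Neutropenia:** the definitions in 6.12 and 8.6 include fever, which a laboratory value cannot supply. Report neutrophil-count grades separately from those fever-based grades, and reconcile the passages.

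The cost is one question at contacts already planned, slightly more data entry and a short grading program. Reported low-grade rates will rise in both arms.

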#### 12.3 Treatment procedure

[Refer to Appendix 2 for a summary chart of study assessments]

Participants entered into the study will be randomised 1:1 to receive artesunate 200 mg or matched placebo once a day orally for 14 days to commence 15 days prior to day of scheduled surgery. The artesunate/placebo packs dispensed to the participant will provide clear instructions on when to start taking the IMP and when to stop.

Study medication will be started fifteen days before the scheduled surgery with the final dose taken on Day 14 (the day before surgery).

Day 7 of study medication (telephone assessment)

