The Day 28 review may be performed within 7 days of the set date.

The Day 42 review may be performed within 2 weeks of the set date.

The 6 to 60 month follow up visits post surgery may be performed +/- 6 weeks of the set date.

If for any reason study follow up visits defer from the scheduled study time scales (for example the 12 month follow up visit is scheduled before the timeframe window due to a rising CEA or post adjuvant chemotherapy) this will be at the managing clinicians discretion. However a minor Deviation Reporting Form should be completed to document the reason for the deviation and reported according to SOP.

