## Surgical morbidity/mortality

The proportion of patients experiencing an adverse event in relation to surgical morbidity/mortality will be compared between the two treatment arms using the chi-squared test. When cell frequencies are less than 5, Fisher's exact test will be used. The chi-squared test for trend will also be used to compare rates of adverse events. Length of hospital stay will be reported as a mean.

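### The cut-off for adverse-event collection is tied to the drug schedule, not the operation, so observation for surgical morbidity varies with delay to surgery and the timing of the Day 42 review

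*Protocol*

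**What the plan says.** Section 14.1 (Definitions) sets the pharmacovigilance window: adverse events are "collected from the day 1 of IMP dose until 4 weeks following the end of the IMP 14 day treatment schedule". It adds: "This coincides with the D42 post surgical review".

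Section 12.3 gives the calendar. It places the operation at "Day 15 Surgery" and labels the later visit "Day 42 (Routine follow up 4 weeks post surgery"). The visit windows in the same section add: "The Day 42 review may be performed within 2 weeks of the set date". Appendix 2 shows the same tolerance of 2 weeks either side.

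Section 12.3 names adverse events at Day 7, at Day 14, and in the period after surgery or during the in-patient stay, with an alternative time point if surgery is cancelled. That post-operative item has no end date. Day 28 lists a full blood count only. Day 42 lists medical history and blood tests. The Appendix 2 chart has no adverse-event row.

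Surgical complications are a secondary objective (section 5), and surgical morbidity/mortality is a secondary endpoint (sections 5.1 and 17.2.2). Section 17.3.3.3 analyses it from adverse events: "The proportion of patients experiencing an adverse event in relation to surgical morbidity/mortality will be compared between the two treatment arms", by chi-squared or Fisher's exact test. The section gives no post-operative period for the count.

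**The concern.** A complication rate compared as a simple proportion needs the same length of observation after the operation in every patient, or at least the same distribution of lengths in both arms. Here the only stated cut-off for adverse events counts from the end of the 14-day drug schedule. If the operation moves and the cut-off does not, the post-operative part of the window shrinks.

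The delay need not be unrelated to treatment. Section 6.12 names neutropenia and haemolytic anaemia as the main possible risks. Section 12.3 states: "Safety blood tests (FBC, U&E, LFT) must be available prior to patients having surgery to exclude risk of neutropenia and deranged biochemistry". In the pilot study described in section 6.8, two patients on artesunate had Grade 3 neutropenia and anaemia and were transfused before going on to surgery. If such events postpone surgery more often on artesunate, that arm is watched for less time after surgery and some of its complications may go uncounted. The question at stake is whether artesunate before surgery increases surgical complications.

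This has to be settled in the protocol. A later analysis plan can define an analysis window, but it cannot recover events that sites were not asked to collect.

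**Working it through.** **Inputs**
- End of drug schedule: Day 14; collection continues for 4 weeks, or 28 days (14.1).
- Planned surgery: Day 15 (12.3).
- Review: Day 42, allowed 14 days either side (12.3, Appendix 2).
- Delay to surgery, d days: not given in the documents. The values below are assumptions that show the range.

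**Step 1. Reproduce the stated cut-off.** 14 + 28 = Day 42. This agrees with section 14.1's equation of the window with the Day 42 review.

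**Step 2. Literal reading: collection stops on Day 42.** Post-operative days = 42 − (15 + d) = 27 − d, with a minimum of 0.

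| Delay d (assumed) | Post-operative days covered |
|---|---|
| 0 | 27 |
| 3 | 24 |
| 7 | 20 |
| 14 | 13 |
| 21 | 6 |
| 27 | 0 |

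**Step 3. Alternative reading: collection runs to the actual review.** The review may be held from 42 − 14 = Day 28 to 42 + 14 = Day 56. With surgery on Day 15, coverage is 28 − 15 = 13 days to 56 − 15 = 41 days.

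Steps 2 and 3 are alternatives and should not be combined. If the cut-off is fixed at Day 42, an early review does not shorten it. If the review is the cut-off, a late review lengthens it.

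**Step 4. Compare with the protocol's own label.** Four weeks after surgery on Day 15 is 15 + 28 = Day 43. On schedule the gap is therefore 43 − 42 = 1 day. The nominal length is not the problem; the anchor is.

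**Step 5. A small inconsistency in the calendar.** Section 12.3 also says: "Study medication will be started fifteen days before the scheduled surgery with the final dose taken on Day 14 (the day before surgery"). A start on Day 1, fifteen days ahead, puts surgery on Day 16, while the second half of the sentence puts it on Day 15. With Day 16 the literal coverage is 42 − 16 = 26 days. The two statements need to be reconciled; the difference is one day and does not change the point.

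**Step 6. Effect of anchoring to surgery.** With a cut-off at surgery + 28 days, every operated patient has 28 days whatever the delay. On schedule that is 1 day more than now. With surgery + 30 days it is 30 − 27 = 3 days more.

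**The case against.** The strongest reply is that the protocol is less rigid than the literal rule in 14.1. Section 12.3 asks for adverse events after surgery and during the in-patient stay, with no end date and with provision for cancelled surgery. It labels the Day 42 visit by its distance from the operation, and 14.1 calls it a post-surgical review, so the visit may have been meant to follow the operation. Section 14.2 has all adverse events entered in the hospital notes and the CRF, and medical history is taken at Day 42. Section 11.3 calculates the start of dosing from the surgery date, so rescheduling before the first dose moves both. Section 17.3.3.3 does not itself say that morbidity is confined to the 14.1 window.

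Most of this stands, and it limits the point in three places where a reader might infer more.

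- A reader might take 27 days as a ceiling. It is the on-schedule value under the literal rule; a review held late could extend coverage to 41 days.
- A reader might conclude that complications after discharge are lost in general. On schedule the 27 days include time after discharge, and in-patient events after a delayed operation are probably caught by 12.3. What is exposed is mainly the post-discharge period after delayed surgery or, if the visit is the cut-off, after an early review.
- A reader might conclude that the comparison is already tilted in favour of artesunate. That needs delay after dosing starts that differs by arm. The documents give no delay rate. Section 12.3 requires results before surgery but states no hold, and both pilot patients went on to surgery without further complications.

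The mortality half of the endpoint is not affected, because section 14.2 has all deaths reported with no time limit.

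None of this supplies a stated surgery-anchored period for morbidity, or an adverse-event item at Day 28 or at the Day 42 visit on which 14.1 relies.

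**Conclusion.** The point holds as an inconsistency with a cheap remedy, not as a demonstrated bias. Sections 14.1 and 12.3 and the Day 42 visit window give different answers to when adverse-event collection ends after surgery. Depending on the reading, an on-time patient is covered for 27 days or for anything from 13 to 41; under the literal rule each day of delay costs one day. Against the protocol's own 4-week label the on-schedule shortfall is 1 day.

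The consequence for the surgical-morbidity comparison is conditional. It rests on two assumptions: that morbidity is counted from adverse events collected under 14.1, which is a reasonable inference because no other cut-off is stated, and that delay differs between arms. The second cannot be sized from the documents, so no trial-level effect can be given.

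**What to change.** 1. In section 14.1, continue adverse-event collection until Day 42 or the end of a fixed post-operative period, whichever is later. The period could be the protocol's own 4 weeks after surgery, or 30 days.
2. In section 17.3.3.3, compare surgical morbidity over that same period, counted from the day of surgery, in both arms.
3. In section 12.3, add adverse events to the Day 28 and Day 42 lists, and add an adverse-event row to Appendix 2.
4. Where the Day 42 review takes place before the post-operative period ends, because the review is early or surgery was delayed, have the site complete adverse-event follow-up by telephone or from the notes.
5. Reconcile the Day 15 and Day 16 statements of the surgery day in section 12.3, so that the period has one starting point.

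The cost is protocol wording, one CRF field, 1 to 3 more days of collection for a patient on schedule, and a call or note review for early reviews and delayed operations. Sample size and the primary analysis do not change.
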